Clinical Study Protocol

Drug Substance Durvalumab (MEDI4736)

Study Number **19-20015**

Edition Number: **4**

Date: **11 February 2022**

Investigational Drug **Durvalumab (MEDI4736)**

Substance(s) **Sirolimus (Rapamune)**

Study Number **19-20015**

Version Number **4**

Date

11 February 2022

A Phase 1b Neoadjuvant Trial of Sirolimus Followed by Durvalumab (MEDI4736) in Resectable Non-small Cell Lung Cancer

Supporter: AstraZeneca/MedImmune

Clinical Study Protocol

Drug Substance Sirolimus (Rapamune)

Study Number **19-20015**

Edition Number: 4

Date: 11 February 2022

PROTOCOL SYNOPSIS

Clinical Protocol ESR 19-20015

Study Title: A Phase 1b Neoadjuvant Trial of Sirolimus followed by Durvalumab (MEDI4736) in Resectable Non-small Cell Lung Cancer

Protocol Number: 19-20015

Clinical Phase: Ib

Study Duration: 4 years, which will include survival follow-up for up to 2 years after the last patient receives the last dose of neoadjuvant durvalumab

Investigational Product(s) and Reference Therapy:

Durvalumab (MEDI4736) solution for infusion after dilution will be supplied in glass vials containing 500 mg of liquid solution durvalumab at a concentration of 50 mg/mL infusion after dilution.

Sirolimus (Rapamune) will be supplied in 1 mg, white, triangular-shaped tablets marked “RAPAMUNE 1 mg” on one side; bottle containing 100 tablets.

Research Hypothesis

We hypothesize that administration of sirolimus, an mTOR inhibitor, followed by durvalumab, an engineered human IgG1 kappa monoclonal antibody targeting PD-1, will demonstrate a good safety profile and produce objective responses in clinical Stage I-IIIA NSCLC. We plan to assess established markers that correlate with response including PD-L1 expression in the tumors and tumor mutation burden by next generation sequencing. As these markers are not perfect and some patients with low PD-L1 and mutational burden may derive benefit, additional study of immune mechanisms is needed. Moreover, there is significant interest in developing combination therapy regimens that enhance the immune system response to cancer of patients that are PD-L1 and mutational burden low. Our focus on biomarkers of response will help identify patients who will benefit from this treatment strategy.

Objectives:

Co-Primary Objectives:

- To evaluate the safety and tolerability of sirolimus followed by durvalumab as neoadjuvant treatment

Clinical Study Protocol

Drug Substance Sirolimus (Rapamune)

Study Number **19-20015**

Edition Number: **4**

Date: **11 February 2022**

- To evaluate the efficacy of sirolimus followed by durvalumab as neoadjuvant treatment for Stage I, II, and IIIA NSCLC

Secondary Objective(s):

- To evaluate the efficacy of sirolimus followed by durvalumab as neoadjuvant treatment for Stage I, II, and IIIA NSCLC
- To evaluate response to sirolimus followed by durvalumab in patients with PD-L1 positive vs. PD-L1-negative tumors
- To evaluate the association between blood mutation burden and response to sirolimus followed by durvalumab

Exploratory Objective(s):

- To evaluate the immune-mediated effects of sirolimus followed by durvalumab
- To investigate tumor and immune microenvironment changes in tissue samples

Study Design:

Up to 31 patients with NSCLC will be enrolled in this study at Emory University Winship Cancer Institute and associated clinical sites. Eligible patients will complete 3 weeks of daily oral sirolimus followed by 2 cycles of durvalumab treatment prior to proceeding to standard of care surgical resection. Durvalumab will be administered at a dose of 1500mg Q 3 weeks starting on C1D1 for up to 2 cycles that are 21 days in length. Pharmacodynamic analysis will be done using PD samples collected at baseline (tissue) and with blood samples on day 1, day 22 C1 prior to durvalumab, day 43 C2 durvalumab, and at the time of surgery (blood and tissue). Additional post surgery blood samples will be collected at 1-, 3-, and 6-months post-surgery. See Appendix D for schedule of Biomarker collection. Patients will proceed to surgery within a 2–3-week period post 2nd dose of durvalumab but not earlier than two weeks after the administration of durvalumab i.e. not earlier than C2D14. Additionally, as an optional study, patients will self-administer heavy water (D2O) 50ml orally three times a day from day 22 C1 through day 27 followed by 50ml orally twice a day through the day prior to surgery in order to label dividing cells for research tracking purposes.

Number of Centers: Emory University Winship Cancer Institute and affiliated hospitals

Number of Patients: 31

Study Population: Resectable Stage 1-3A NSCLC

Inclusion Criteria:

- Pathologically documented NSCLC who are candidates for surgical resection
- Capable of signing informed consent

- Age \geq 18 years at time of study entry.
- Eastern Cooperative Oncology Group (ECOG) performance status of 0 or 1
- Life expectancy of \geq 26 weeks
- Body weight >30 kg
- Adequate normal organ and marrow function as defined in protocol
- Evidence of post-menopausal status or negative urinary or serum pregnancy test for female pre-menopausal patients.
- Measurable disease defined by RECIST v 1.1.
- Patient is able to take oral medications
- Patient consents to heavy water (D2O) self-administration, if enrolling in optional heavy water study
- Patient is willing and able to comply with the protocol for the duration of the study including undergoing treatment and scheduled visits and examinations including follow up.

Exclusion Criteria:

- Prior therapy for lung cancer including chemotherapy, hormonal therapy, or radiotherapy.
- Concurrent enrolment in another clinical study, unless it is observational
- Prior treatment with anti-PD-1, anti-PDL-1, including durvalumab other PD-1/PDL-1 pathway targeting agents, or mTOR inhibition.
- History of allogenic organ transplantation.
- Active or prior documented autoimmune or inflammatory disorders (including inflammatory bowel disease [e.g., colitis or Crohn's disease], systemic lupus erythematosus, Sarcoidosis syndrome, or Wegener syndrome [granulomatosis with polyangiitis, Graves' disease, rheumatoid arthritis, hypophysitis, uveitis, etc]). Exceptions listed in protocol below.
- Uncontrolled intercurrent illness
- History of another primary malignancy with exceptions noted in protocol
- QT interval corrected for heart rate using Fridericia's formula (QTcF) \geq 470 ms
- History of active primary immunodeficiency
- Active infection including tuberculosis, hepatitis B, hepatitis C
- Current or prior use of immunosuppressive medication within 14 days before the first dose of durvalumab. There are exceptions to this criterion listed below in the protocol
- Receipt of live attenuated vaccine within 30 days prior to the first dose of study medications

- Female patients who are pregnant or breastfeeding or male or female patients of reproductive potential who are not willing to employ effective birth control from screening to 90 days after the last dose of durvalumab
- Known allergy or hypersensitivity to any of the study drugs or excipients.
- Patients with a history of idiopathic pulmonary fibrosis, pneumonitis (including drug induced), organizing pneumonia, or evidence of active pneumonitis on screening chest CT scan
- Judgment by the investigator that the patient is unsuitable to participate in the study and the patient is unlikely to comply with study procedures, restrictions and requirements.

Investigational Product(s), Dose and Mode of Administration:

Patients will receive 1500 mg durvalumab via IV infusion Q3W for up to a maximum of 2 cycles prior to curative resection surgery. Weight-based dosing (20 mg/kg) should be utilized for patients whose body weight falls to <30 kg while on study.

Patient will self-administer sirolimus 6 mg orally once on day 1, followed by once daily dosing of 2mg, continuously through day 21, which is one day prior to C1 of durvalumab. The dose should be taken each morning, with or without food.

Study Assessments and Criteria for Evaluation:

Safety Assessments:

- Incidence of adverse events, with severity per NCI CTCAE v5.0
- Length of hospital stay after surgery

Efficacy Assessments:

- Complete pathologic response, scored by a pathologist, based on surgical resection as defined by prior studies
- Investigator-assessed response rate per RECIST v1.1
- DFS and OS
- Pathological response in PD-L1-positive and PD-L1-negative groups
- Overall response rate in PD-L1-positive and PD-L1-negative groups based on mutational burden

Statistical Methods and Data Analysis:

Safety Analyses:

All enrolled patients will be evaluable for safety analyses from the time of their first treatment with sirolimus. After study complete, DLTs will be summarized and tabulated by type and grade. DLT rate

by dose level will be calculated as proportion (Patients with DLT/Total patients) along with 95% confidence intervals using the Clopper-Pearson method. Chi-square test or Fisher's exact test will be used to compare the probability of DLT between the different other factors, such as PD-L1 status, dose levels, etc. respectively.

Other adverse events (toxicity) will be listed and summarized overall and by dose level. Adverse events will also be listed by severity, seriousness, and by system organ class. The number and percentage of subjects who experience AEs will be presented in tabular and/or graphical format and summarized descriptively, where appropriate. No formal statistical comparison between the dose levels or PD-L1 will be performed. AEs will be presented with and without regard to causality based on the investigator's judgment. The frequency of overall toxicity, categorized by toxicity grades 1 through 5, will be described. Additional summaries will be provided for AEs that are observed with higher frequency.

Efficacy Analyses:

The primary and secondary efficacy analyses will include all enrolled patients who have received at least one dose of durvalumab, underwent resection and who do not have EGFR mutant tumors (*efficacy population*).

Primary Efficacy Endpoint

The effectiveness of sirolimus followed by durvalumab will be assessed by complete pathologic response rate in the *efficacy population*. If the null hypothesis is rejected then this is evidence that the response rate exceeds 10% when sirolimus followed by durvalumab is given before resection. The one-sided 95% confidence interval (CI) for complete pathologic response will be reported. Exact binomial test will be used to compare the estimated complete pathologic response rate to the historical reference.

Secondary Efficacy Endpoints

The complete pathologic response rates for PDL-1 negative and PDL-1 positive patients in the *efficacy population* will be presented separately.

A comparison of both the *complete pathologic response* and investigator assessed response rates per RECIST v1.1 rates between the PD-L1 positive and PD-L1 negative groups will be performed by calculating the lower bound of a one-sided 80% CI for the difference, complete pathologic response for PDL-1 positive patients – complete pathologic response for PDL-1 negative patients. Chi-square test or Fisher's exact test will be used to compare the efficacy in term of response rate between the different groups stratified by other factors, respectively. Logistics regression model will be further employed to test the adjusted effect of each other factor on the response rate after adjusting for other clinical factors and demographic factors, respectively. Correlation of response will be performed for tumor mutation burden using spearman correlation coefficient and tested with Wald's test.

Sample Size Determination:

Pathologic complete response is rare following neoadjuvant chemotherapy but was reported in 0-8% of cases³⁹. The current study is designed to test improved rate of pathologic complete response from 10% to 25% with sequential treatment with sirolimus and durvalumab. Using a MinMax 2-stage design, a total of 31 patients will be enrolled in 2 stages. At the end of stage I, at least 2 of 16 patients must achieve complete pathologic complete response in order for the study to enroll 15 additional patients. The regimen of sirolimus followed by durvalumab will be considered to have sufficient efficacy to warrant further testing in this patient population if 6 or more of the 31 patients achieve a pathologic CR at the end of stage II. The study has 80% power at a 1-sided alpha of 0.1 to show a compelling 25% pCR compared to a less compelling rate of 10%. Because this is a signal finding study, an alpha of 0.1 is considered reasonable since any promising signal will be confirmed in a larger follow-up study.

Clinical Study Protocol

Drug Substance Sirolimus (Rapamune)

Study Number **19-20015**

Edition Number: **4**

Date: **11 February 2022**

SCHEDULE OF STUDY ASSESSMENTS

	Screening	Sirolimus	Durvalumab C1	Durvalumab C2	Pre- surgery	Surgery	Study DC	Follow- up	For details see Section				
Week	-4 to 0	0	3	6	8-9		Post Surgery 30 +/- 7 days	Every 3 months for 2 years					
Day	-28 to 0	1-21	22 +/- 3 days^a	43 +/- 3 days^a	57-64 +/- 10 days								
Informed Consent													
Informed consent: study procedures ^b	X								Error! Referen ce source not found. Error! Referen ce source not found.				

Clinical Study Protocol

Drug Substance Sirolimus (Rapamune)

Study Number **19-20015**

Edition Number: **4**

Date: **11 February 2022**

	Screening	Sirolimus	Durvalumab C1	Durvalumab C2	Pre- surgery	Surgery	Study DC	Follow- up	
Week	-4 to 0	0	3	6	8-9		Post Surgery 30 +/- 7 days	Every 3 months for 2 years	For details see Section
Day	-28 to 0	1-21	22 +/- 3 days^a	43 +/- 3 days^a	57-64 +/- 10 days				
Consent: genetic sample and analysis (optional)	X								Error! Referen ce source not found.
Study Procedures									
Physical exam (full)	X								Error! Referen ce source not found.
Targeted physical exam (symptom driven)		X	X	X	X	X	X		Error! Referen ce source not found.

Clinical Study Protocol

Drug Substance Sirolimus (Rapamune)

Study Number **19-20015**

Edition Number: **4**

Date: **11 February 2022**

	Screening	Sirolimus	Durvalumab C1	Durvalumab C2	Pre- surgery	Surgery	Study DC	Follow- up	For details see Section	
Week	-4 to 0	0	3	6	8-9		Post Surgery 30 +/- 7 days	Every 3 months for 2 years		
Day	-28 to 0	1-21	22 +/- 3 days ^a	43 +/- 3 days ^a	57-64 +/- 10 days					
Vital signs ^c	X	X	X	X	X		X		Error! Referen ce source not found.	
ECG ^d	X	As clinically indicated							Error! Referen ce source not found.	
Concomitant medications		<----->							Error! Referen ce source not found.	

Clinical Study Protocol

Drug Substance Sirolimus (Rapamune)

Study Number **19-20015**

Edition Number: **4**

Date: **11 February 2022**

	Screening	Sirolimus	Durvalumab C1	Durvalumab C2	Pre- surgery	Surgery	Study DC	Follow- up	For details see Section	
Week	-4 to 0	0	3	6	8-9		Post Surgery 30 +/- 7 days	Every 3 months for 2 years		
Day	-28 to 0	1-21	22 +/- 3 days ^a	43 +/- 3 days ^a	57-64 +/- 10 days					
Demography, including baseline characteristics and tobacco use	X								Error! Reference source not found.	
Eligibility criteria	X								Error! Reference source not found. and Error! Reference source not found.	
Laboratory Assessments										

Clinical Study Protocol

Drug Substance Sirolimus (Rapamune)

Study Number **19-20015**

Edition Number: **4**

Date: **11 February 2022**

	Screening	Sirolimus	Durvalumab C1	Durvalumab C2	Pre- surgery	Surgery	Study DC	Follow- up	For details see Section	
Week	-4 to 0	0	3	6	8-9		Post Surgery 30 +/- 7 days	Every 3 months for 2 years		
Day	-28 to 0	1-21	22 +/- 3 days ^a	43 +/- 3 days ^a	57-64 +/- 10 days					
Clinical chemistry ^e	X	X ^f	X	X	X		X		Error! Referen ce source not found.	
Hematology ^e	X	X ^f	X	X	X		X		Error! Referen ce source not found.	
TSH ^g , (reflex free T4 ^h)	X			X	X		X		Error! Referen ce source not found.	

Clinical Study Protocol

Drug Substance Sirolimus (Rapamune)

Study Number **19-20015**

Edition Number: **4**

Date: **11 February 2022**

	Screening	Sirolimus	Durvalumab C1	Durvalumab C2	Pre- surgery	Surgery	Study DC	Follow- up	For details see Section	
Week	-4 to 0	0	3	6	8-9		Post Surgery 30 +/- 7 days	Every 3 months for 2 years		
Day	-28 to 0	1-21	22 +/- 3 days^a	43 +/- 3 days^a	57-64 +/- 10 days					
Hepatitis B and C and HIV	X								Error! Referen ce source not found.	
Pregnancy test ⁱ	X		X						Error! Referen ce source not found.	
Sirolimus level for batch analysis			X						8.1.2	
Monitoring										
WHO/ECOG performance status	X	X	X	X	X	X	X	X	10.1.1	

Clinical Study Protocol

Drug Substance Sirolimus (Rapamune)

Study Number **19-20015**

Edition Number: **4**

Date: **11 February 2022**

	Screening	Sirolimus	Durvalumab C1	Durvalumab C2	Pre- surgery	Surgery	Study DC	Follow- up	For details see Section									
Week	-4 to 0	0	3	6	8-9		Post Surgery 30 +/- 7 days	Every 3 months for 2 years										
Day	-28 to 0	1-21	22 +/- 3 days^a	43 +/- 3 days^a	57-64 +/- 10 days													
AE/SAE assessment ^j		<----->																
IP administration																		
Sirolimus		X							5.1									
Durvalumab ^k			X	X					5.2									
Optional Heavy Water (D2O)			X	X	X													

Clinical Study Protocol

Drug Substance Sirolimus (Rapamune)

Study Number **19-20015**

Edition Number: **4**

Date: **11 February 2022**

	Screening	Sirolimus	Durvalumab C1	Durvalumab C2	Pre- surgery	Surgery	Study DC	Follow- up	For details see Section				
Week	-4 to 0	0	3	6	8-9		Post Surgery 30 +/- 7 days	Every 3 months for 2 years					
Day	-28 to 0	1-21	22 +/- 3 days^a	43 +/- 3 days^a	57-64 +/- 10 days								
Other assessments and assays													
Blood biomarker samples for immunologic analysis		X	X	X	X		X	X ^m	Error! Reference source not found.E rror! Reference source not found.				

Clinical Study Protocol

Drug Substance Sirolimus (Rapamune)

Study Number **19-20015**

Edition Number: **4**

Date: **11 February 2022**

	Screening	Sirolimus	Durvalumab C1	Durvalumab C2	Pre- surgery	Surgery	Study DC	Follow- up	For details see Section	
Week	-4 to 0	0	3	6	8-9		Post Surgery 30 +/- 7 days	Every 3 months for 2 years		
Day	-28 to 0	1-21	22 +/- 3 days^a	43 +/- 3 days^a	57-64 +/- 10 days					
Tumor biopsy (newly acquired/fresh if amenable to core biopsy)	X								Error! Reference source not found. Error! Reference source not found.	
Tumor biopsy (archival, required for diagnosis and PD-L1 assessment)	X								Error! Reference source not found.	
Fresh tumor and lymph node samples for immunologic analysis						X				
Efficacy evaluations										

Clinical Study Protocol

Drug Substance Sirolimus (Rapamune)

Study Number **19-20015**

Edition Number: **4**

Date: **11 February 2022**

	Screening	Sirolimus	Durvalumab C1		Durvalumab C2		Pre- surgery	Surgery	Study DC	Follow- up	For details see Section	
Week	-4 to 0	0	3		6		8-9		Post Surgery 30 +/- 7 days	Every 3 months for 2 years		
Day	-28 to 0	1-21	22 +/- 3 days^a		43 +/- 3 days^a		57-64 +/- 10 days					
Tumor evaluation (CT or MRI) (RECIST 1.1) ¹ within 6 weeks of C1D1	X ^b						X				Error! Referen ce source not found.	
Pathologic response assessment								X				

^a If cycle 2 day 1 visit is delayed, all subsequent visits will be delayed accordingly

^b Informed consent of study procedures and tumor biopsy sample may be obtained prior to the 28-day screening window, if necessary, in order to permit tumor biopsy sample acquisition and analysis prior to randomization. The collection of tumor biopsies at the time of progression prior to retreatment is mandated; the Investigator must consult with the Study Physician if such sampling is not feasible. If laboratory or imaging procedures were performed for alternate reasons prior to signing consent, these can be used for screening purposes with consent of the patient. However, all screening laboratory and imaging results must have been obtained within 28 days of study assignment.

^c Body weight is recorded at each visit along with vital signs

^d Any clinically significant abnormalities detected require triplicate ECG results.

^e Serum or plasma clinical chemistry (including LFT monitoring) and hematology may be performed more frequently if clinically indicated.

^f If screening clinical chemistry and haematology assessments are performed within 3 days prior to Day 1 (first infusion day), they do not need to be repeated at Day 1.

^g If TSH is measured within 14 days prior to Day 1 (first infusion day), it does not need to be repeated at day 1.

^h Free T4 may only be measured if TSH is abnormal or if there is clinical suspicion of an AE related to the endocrine system.

Clinical Study Protocol

Drug Substance Sirolimus (Rapamune)

Study Number **19-20015**

Edition Number: **4**

Date: **11 February 2022**

- ⁱ For women of childbearing potential only. A urine or serum pregnancy test is acceptable. Women of childbearing potential are required to have a pregnancy test within 7 days prior to the first dose of study drug. Pregnancy test may occur on Day 1, but results must be available and reviewed by the treating physician or Investigator prior to commencing an infusion
- ^j For AEs/SAEs reported during screening, additional information such as medical history and concomitant medications may be needed
- ^k Results for LFTs, electrolytes, full blood count and creatinine must be available before commencing an infusion (within 3 days) and reviewed by the treating physician or Investigator prior to dosing.
- ^l RECIST assessments will be performed on images from CT (preferred) or MRI, each preferably with IV contrast of the chest, abdomen (including liver and adrenal glands) and pelvis. Pelvic imaging is recommended only when primary or metastatic disease in the pelvic region is likely. Additional anatomy should be imaged based on signs and symptoms of individual patients at baseline and follow-up. Baseline assessments should be performed no more than 28 days before the date of randomization and, ideally, should be performed as close as possible to and prior to the start of IP. Repeat assessments will be performed as close as possible to surgery date.
- ^m Peripheral blood collection for biomarker analysis will be obtained at 3- and 6-months post-surgery
- ⁿ Screening/Baseline Cross-sectional Imaging (CT, PET, or MRI) for RECIST should be within 6 weeks of starting C1D1 of trial therapy

Note: All assessments on treatment days are to be performed prior to infusion, unless otherwise indicated.

C Cycle; ECG Electrocardiogram; IM Intramuscular; LFT Liver function test; T₄ Thyroxine; TSH Thyroid-stimulating hormone.

Clinical Study Protocol

Investigational Drug Substance: MEDI4736 Sirolimus (Rapamune)

Study Number **19-20015**

Edition Number: 4

Date: **11 February 2022**

TABLE OF CONTENTS

PAGE

PROTOCOL SYNOPSIS	2
SCHEDULE OF STUDY ASSESSMENTS	8
TABLE OF CONTENTS	12

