Table 1: Neoadjuvant Study Treatment dosing regimen

Regimen Description					
Agent	Premedications Precautions	Dose	Route	Schedule	Cycle Length
Sirolimus	Take with or without food	6 mg on day 1, followed by 2mg	PO	Once daily Start on day 1	21 days (3 weeks)

Clinical Study Protocol

Investigational Drug Substance: MEDI4736 Sirolimus (Rapamune)

Study Number **19-20015**

[figure not shown]
Edition Number: 4

Date: **11 February 2022**

		daily on days 2-21			
Durvalumab	None required	1500 mg in NS or D5W	IV over 1 hr	Once every 3 weeks, starting on day 22	

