5.2.2 Doses and treatment regimens

The dose of sirolimus for this study is 6mg orally daily once on day 1, followed by 2mg orally daily from day 2 through 21.

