5.2.4 Monitoring of dose administration

The patient will be requested to maintain a medication diary of each dose of medication. The medication diary will be returned to clinic staff at the end of each course.

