8. STUDY PROCEDURES

8.1 Schedule of study procedures

Before study entry, throughout the study, and following study drug discontinuation, various clinical and diagnostic laboratory evaluations are outlined. The purpose of obtaining these detailed measurements is to ensure adequate safety and tolerability assessments. Clinical evaluations and laboratory studies may be repeated more frequently if clinically indicated. The Schedules of Assessments during the screening and treatment period is provided following the Protocol Synopsis.

- Tumor efficacy (RECIST) assessment dates are not affected by dose delays and remain as originally scheduled, as they are based on the date of surgery.
- All other scheduled assessments must be performed relative to the start of the dosing cycle such that all laboratory procedures, etc. required for dosing should be performed within 3 days prior to dosing.
- Patients may delay durvalumab dosing under certain circumstances.
 - Dosing may be delayed per Toxicity Management Guidelines, due to either an immune or a non-immune-related AE.
 - If dosing must be delayed for reasons other than treatment-related toxicity, dosing will resume as soon as feasible

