8.1.2 Treatment phase

Procedures to be conducted during the treatment phase of the study are presented in the Schedule of Assessments. Screening procedures performed within 72 hours of cycle 1 day 1 do not need to be repeated on cycle 1 day 1.

1. Sirolimus dosing: will be given 6mg po once on day 1, followed by 2mg po daily on days 2-21. Steady state trough levels will be collected on day 23 and stored for batch analysis.
2. Heavy water dosing: first dose to be taken in clinic on day 23 and a 6 week supply for self- administration will be dispensed in labeled conical tubes. The patients will also be shown how to collect salivate samples.
3. Durvalumab dosing: starting on Day 22 q 3 weeks for 2 doses
4. Restaging imaging prior to surgery
5. Standard of care surgical resection
6. Peripheral blood research tube collection per study calendar

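### Minor wording conflicts at the sirolimus-to-durvalumab hand-over: trough on day 22 or day 23, a C1 window that does not exclude days 19-21, and a statement that no overlapping toxicities are expected

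*Combined protocol and SAP*

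**What the plan says.** **Dosing order.** The dosing text is consistent. The synopsis design paragraph says "Eligible patients will complete 3 weeks of daily oral sirolimus followed by 2 cycles of durvalumab treatment", and its dosing paragraph takes sirolimus "continuously through day 21, which is one day prior to C1 of durvalumab". Section 5.2.2 gives the loading dose on day 1, "followed by 2mg orally daily from day 2 through 21". Table 1 and Section 5.1.2 give durvalumab "Once every 3 weeks, starting on day 22", and Section 8.1.2 has it "starting on Day 22 q 3 weeks for 2 doses".

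**Window.** The Schedule of Study Assessments heads the Durvalumab C1 column as day 22 ± 3 days, and the durvalumab administration row sits in that column. The sirolimus column is a fixed 1-21. The text on moved infusions deals only with delay: "Patients may delay durvalumab dosing under certain circumstances" (Section 8.1) and, in footnote a, "If cycle 2 day 1 visit is delayed, all subsequent visits will be delayed accordingly".

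**Trough.** Section 8.2.3 (Sirolimus Level Collection) schedules the level on day 22, after a last dose on day 21, yet asks the patient to come with that morning's dose. Section 8.1.2 collects it on day 23. The schedule row for the level is in the C1 column but refers the reader to 8.1.2. Section 8.1.2 also starts heavy water on day 23, where the synopsis and Section 5.3 say day 22.

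**Toxicity.** Section 6.4.3 expects no overlapping toxicities. Sections 1.6.2.1 and 1.6.2.2 each list pneumonitis/ILD, diarrhea, hypersensitivity and infection, one for durvalumab and the other for sirolimus.

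**The concern.** Sites work from the schedule and the procedures section, and here the two disagree with each other or with the dosing rule.

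- **Trough.** Section 3.1 describes a regimen meant to reach 5-15 ng/ml. If some sites sample at 24 h and others at 48 h, the levels are not comparable, and a 48 h sample is not the trough of a once-daily regimen. A patient told to bring a morning dose on day 22 might take a 22nd dose on the infusion day.
- **Window.** Section 3.1 gives the reason for the lead-in: to separate what sirolimus contributes from what durvalumab contributes. An infusion on days 19-21 would either leave sirolimus doses on or after the infusion day or cut the 21-day course short. A site could regard it as in window, so it might not be logged as a deviation.
- **Toxicity.** These patients are going to lung resection, and Section 1.6.2 says the risks of the combination are not known. The toxicity-management section should not contradict the risk section.

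**Working it through.** **Plan's own gap.** Last sirolimus day 21 (5.2.2), first durvalumab day 22 (5.1.2, Table 1): 22 − 21 = 1 day, as the synopsis states.

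**Trough.** Inputs: last dose day 21 (8.2.3); half-life 62 ± 16 h, measured in stable renal-transplant patients (1.6.2.2, Excretion); median trough 6.8 ng/mL, interquartile range 4.6 to 9.0, on 2 mg/day in lymphangioleiomyomatosis (3.1). Assumption: single-exponential decay.

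- Time since last dose: day 22 = 24 h; day 23 = 48 h.
- Ratio of day-23 to day-22 level = 2^(−24/T).
- T = 62 h: 0.765, or 23.5% lower. T = 46 h: 0.697, or 30.3% lower. T = 78 h: 0.808, or 19.2% lower.
- Applied to the cited median: 6.8 × 0.765 = 5.20 ng/mL (6.8 × 0.697 = 4.74; 6.8 × 0.808 = 5.49).

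**Window.** 22 ± 3 gives days 19 to 25. The days shared with sirolimus days 1-21 are 19, 20 and 21.

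- Scheduled sirolimus doses on or after infusion day d = 21 − d + 1, which is 3, 2 and 1 for days 19, 20 and 21.
- Full course = 6 + 20 × 2 = 46 mg. The doses at issue are 6, 4 or 2 mg: 6/46 = 13.0%, 4/46 = 8.7%, 2/46 = 4.3%.
- If those doses are dropped instead, the course is 18, 19 or 20 days.

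Some co-exposure exists by design. Sirolimus remaining t hours after the last dose = 2^(−t/T), which at 24 h is 76% for T = 62 h (70% for 46 h; 81% for 78 h). With a 0/+3 infusion window the gap is 1 to 4 days, and at T = 62 h the fraction remaining runs from 76% (24 h) to 34% (96 h). The limit therefore protects the order of the drugs; it does not give a uniform gap or a washout.

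**Design.** At least 2 of 16, then at least 6 of 31 responders, gives an exact type I error of 0.079 at 10% and power of 0.805 at 25%. This matches the stated design, and none of the three points enters it.

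**Toxicity.** No arithmetic applies. Each of the four toxicities appears under both drugs in 1.6.2, so the sentence in 6.4.3 cannot stand beside those lists.

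**The case against.** The strongest reply is that the dosing text is specific and repeated, so an infusion on days 19-21 would breach it. The ± 3 is a column header covering every C1 row, and its early side has an innocent use: Section 8.1 and footnote k allow pre-dose laboratory work within 3 days before dosing. All text on moved infusions speaks of delay. This stands, and it rules out a reading that someone might take from the header: that the plan directs concurrent dosing, or that 3 of 7 days means a comparable share of patients. The documents give no frequency of early infusion. What remains is that the infusion row has no window of its own and no rule says which text governs. The diary ("The patient will be requested to maintain a medication diary of each dose of medication") and the infusion record in 5.1.5 would show an early infusion afterwards, but Section 11.2 lists major deviations only.

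On the trough, Section 3.1 makes no individual dose changes, samples are stored for batch analysis, and Section 11 names no analysis of the level. Table 10 counts one level per patient, but the sentence above it allows further draws. A reader might infer from the 5.2 ng/mL figure that exposure would miss its target. That does not follow: the lower quartile in the cited population, 4.6 ng/mL, is already below 5 without the day-23 shift, and the half-life comes from transplant patients.

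On 6.4.3, a reader might infer that pneumonitis goes unmanaged. It does not. Section 6.3 counts Grade 3 and persistent Grade 2 pneumonitis as DLTs, 10.2.3 lists pneumonitis/ILD as an AESI with a work-up, and exclusion criterion 16 removes patients with a history of it.

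**Conclusion.** The point holds as three minor corrections to text that is wrong as written.

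- **Trough.** Sections 8.1.2 and 8.2.3 conflict. A day-23 draw would read about 24% lower (19-30%) than the intended 24 h trough, assuming first-order decay and that the quoted half-life carries over to these patients. Only the description of exposure is affected.
- **Window.** The C1 header fails to exclude an infusion that the dosing text forbids. It is an unreconciled allowance and not an instruction. At most 3 doses (6 of 46 mg) per patient are at issue. Alpha, power and the planned analyses do not change.
- **Toxicity.** Section 6.4.3 contradicts the protocol's own risk lists. Other sections already carry the pneumonitis safeguards, so this is a correction of safety wording.

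**What to change.** 1. In 8.1.2, change the trough to day 22, before the infusion and 24 h after the last dose. In 8.2.3 (Sirolimus Level Collection), delete the request to bring the morning dose, and keep its provision for a separate draw if durvalumab is delayed. In 8.1.2, also move the first heavy-water dose from day 23 to day 22, to agree with the synopsis and 5.3.
2. Leave the C1 column at ± 3 for the other assessments, so that early pre-dose laboratory work stays in window. Add a note to the durvalumab administration row: C1 infusion on day 22, window 0/+3 days, and no earlier than the day after the last sirolimus dose.
3. Replace the 6.4.3 sentence with the toxicities listed for both drugs: pneumonitis/ILD, diarrhea, hypersensitivity and infection.

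The cost is a few lines of text and slightly less freedom in booking the first infusion. Under Section 12.4 a non-administrative change needs a written amendment reviewed by the sponsor and the investigator, so these edits could go into the next one. No sample-size or analysis text needs to change.
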